5.4 Planned Sample Size and Study Sites

Planned enrollment is 191 adults. Patients will be randomized in a 2:1 ratio (Clotrimazole 1% otic solution : Placebo), with the aim of including 150 evaluable patients (100 clotrimazole and 50 placebo).

About 17 study sites in Europe (5 in Bulgaria, 2 in Portugal, 5 in Romania and 5 in Spain) will recruit patients. Enrollment will be competitive, i.e., each study site will continue to enroll patients until recruiting the total of 150 evaluable patients.

5.5 Patient Identification and Randomization

Patients will be randomized at Visit 1, after signing informed consent and meeting eligibility criteria. Randomization will be conducted through an Interactive Web Response System (IWRS) include blocking. The IWRS will assign a patient number, which will be used to identify the patient during screening and, if applicable, throughout the duration of the study. Patients who do not meet the inclusion and exclusion criteria will be registered as screen failures through the IWRS.

For patients who have bilateral otomycosis, the ear with a higher TSSS (as defined in Section 7.1.1.5) will be considered the evaluable one. If the TSSS is identical in both ears, the left ear will be selected as the evaluable ear. In either case, the non-evaluable ear will receive the same treatment as the evaluable ear.

6. STUDY MEDICATION

6.1 Identity

Investigational Medication

| | |
|---------------|--|
| Chemical name | Clotrimazole |
| Generic name | Clotrimazole 1% Otic Solution |
| Trade name | Not applicable |
| Dosage form | Auricular solution, sterile |
| Manufacturer | SALVAT |
| Description | Otic solution in single-dose low-density polyethylene (LDPE) translucent vials containing 0.17 mL deliverable volume |

Reference Medication

| | |
|--------------|--|
| Generic name | Saline solution 0.9% |
| Trade name | Not applicable |
| Dosage form | Auricular solution, sterile |
| Manufacturer | SALVAT |
| Description | Otic solution in single-dose low-density polyethylene (LDPE) translucent vials containing 0.17 mL deliverable volume |

6.2 Administration

Study medication will be self-administered by the patient. At Visit 1, a study staff member will instruct the patient in how to open the containers and administer study medication, and will supervise the patient during administration of the first dose.

The method of administration for the investigational medication and the comparator medication will be the same: instillation of one vial in the affected ear canal(s) twice a day (morning and evening, preferably 12 hours apart) for 14 consecutive days. Ear wicks may be used at the Investigator's discretion. Use of ear wicks must be documented in the EDC.

Study medication will be supplied in single-dose vials containing 0.20 mL (approximately 0.17 mL deliverable volume) per vial. A patient kit will contain 6 pouches of 5 vials each, for a total of 30 vials and a plastic bag labeled with the kit number.

A study staff member will open one pouch and remove 2 vials. He or she will place the removed vials in a bag provided with the kit, and store the 2 vials at the study site in a secure location. The

remaining 3 vials will be returned to the pouch, which will be returned to the kit for dispensation to the patient. Patient will receive a kit with 28 vials and the first administration will be at the site.

Patients with bilateral otomycosis will receive 2 kits (2 vials will be removed from each kit and only 56 vials will be provided to the patient). The patient will administer the contents of 1 vial twice daily to the affected ear(s) for fourteen days. Each vial will be an intact unit, and the patient will twist off the top of the vial to administer the study medication. The solution should be warmed by holding the vial in the hand for one or two minutes to avoid dizziness which may result from the instillation of a cold solution. The patient should lie with the affected ear upward, and then the medication should be instilled. The outer ear lobe should then be gently pulled upward and outward. This will allow the ear drops to flow down into the ear canal. This position should be maintained for 1 minute. Repeat, if necessary, for the opposite ear.

The planned maximum exposure to the active ingredient is approximately 1.7 mg of clotrimazole per dose (3.4 mg per day, approximately 47.6 mg of clotrimazole over a 14-day period). This quantity will be double in case of bilateral disease.

6.3 Packaging, Labeling, and Storage

The primary packaging of study medication will be performed by SALVAT, who will supply the investigational medication as pouches of single-dose vials, as described in Section 6.2. SALVAT will send the pouches directly to [REDACTED]. Each individual vial will contain 0.17 mL deliverable volume of Clotrimazole 1% otic solution. The vial is made from LDPE and is manufactured via a blow-fill-seal process. This process seals the vials directly after manufacture and contains the solution within a unit-dose vial that is intact until the user twists off the cap to administer the medication.

[REDACTED] will be responsible for the packaging, labeling and distribution of the study medication. The medication will be packaged in blinded cartons containing labeled pouches with the vials inside.

All study medication supplies must be stored in accordance with the manufacturer's instructions. Until dispensed to the patients, study medication will be stored in a secure area, accessible to authorized personnel only.

Patient must store unused vials in the protective foil pouch.

6.4 Blinding and Breaking the Blind

All study medication products (test and placebo) will have the same packaging and labels.

The boxes in which the study medication is packaged, shipped, and dispensed will be identical in appearance. When patients return their used and unused study medication containers to the study site, they will be encouraged to bring them in the original carton.

Mycological and bacterial samples will be processed by a central laboratory under blinded conditions. The central laboratory will be blinded to the treatment assignment of the patient from whom the sample was taken.

Unblinding of study treatment assignment should be an unusual occurrence, and should be done only in case of an emergency when knowledge of the actual treatment becomes medically necessary to affect treatment options. The investigator will be able to break the blind and get the subject's treatment assignment through ITRS at any time, by completing the required information (e.g the user's password, the patient code concerned by the unblinding request, unblinding

code...). The investigator should not share the unblinded information with SALVAT or [REDACTED] personnel.

6.5 Drug Accountability

[REDACTED] will provide each Investigator with sufficient amounts of the investigational medication (Clotrimazole 1% otic solution) and the placebo (Saline solution 0.9%). The Investigator will confirm receipt of all kits of study medication using the ITRS and will document receipt in the written study files.

The Investigator will dispense the study medication only to patients included in this study and following the procedures described in this study protocol. Each patient will be given only the study medication carrying his/her number. Each dispensing will be documented in the EDC.

Patients will be asked to keep all used and unused study medication vials, and containers and return them to a study staff member at Visit 3 or at last study visit. If patients forget to bring in containers at Visit 3, they must bring them in no later than Visit 4.

All supplies must be accounted for at the end of the study. The Investigator is responsible for ensuring that accurate and adequate records are maintained. These records will include lot numbers, quantities received, dates received, dates dispensed, etc., for the investigational medication (Clotrimazole otic solution) and the placebo (Saline solution). The exact number of vials used in the study must be noted, regardless of whether the study was completed or terminated prematurely. At the time of return, the Investigator must verify that all used and unused supplies of study medication have been returned by the patient and that no remaining supplies are in the patient's possession.

6.6 Compliance

Compliance will be assessed by a review of the number of vials returned. The number of doses the patient actually took during the treatment period will be divided by the number of doses the patient was expected to take during that period. The resulting ratio will be multiplied by 100% to determine percent compliance. Patients will be considered "compliant" if their percent compliance is between 80% and 100%.

6.7 Concomitant Medications

Any medication the patient takes other than the study medication specified in the protocol is considered a concomitant medication. This includes prescribed medications, over-the-counter medications, herbal remedies, etc. All concomitant medications must be recorded in the EDC.

At Visit 1, patients will be asked what medications they are currently taking or have taken during the last 30 days. At Visits 2, 3, and 4, patients will be asked what concomitant medications they are currently taking or have taken since the last visit.

6.7.1 Prohibited Concomitant Medications

The following medications will be prohibited during the study (unless the subject has prematurely discontinued study treatment):

- Any investigational drug.
- Any systemic antimicrobial or antifungal drug.
- Any compound, agent or substance that is applied or instilled to the evaluable ear or surrounding area, except non-bacteriostatic saline solution for potential additional cleaning before taking the sample to be cultured.
- Any topical antimicrobial or antifungal drug when applied to the non-evaluable ear or surrounding area.
- Any systemic analgesic therapy (prescription or over the counter) with anti-inflammatory properties (acetylsalicylic acid for cardiovascular prevention at doses of 325mg or less is allowed). Analgesics without anti-inflammatory properties, such as acetaminophen and anti-inflammatory agents at stable doses at least 30 days prior to enrollment are allowed.
- Any systemic corticosteroid, except nasal or inhaled corticosteroids at stable doses (at least 30 days prior to enrollment).
- Any non-topical antipruritic agent, except antihistamines at stable doses (at least 30 days prior to enrollment).

6.7.2 Rescue Concomitant Medication

Prohibited medication will be considered rescue medication if they meet both of the following criteria:

- Any otic or systemic treatment administered for reasons associated with otomycosis of the evaluable ear (Note – topical products applied in the non-evaluable ear are NOT considered to be rescue medication)
- Started after Visit 1 but before or at Visit 4 (Note – antifungal given after Visit 4 are NOT considered rescue medications)

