### 3.1.3 Handling of Dropouts and Missing Data

Patients with missing efficacy data or indeterminate outcomes will be considered as treatment failures for efficacy analyses.

For the primary and secondary endpoints, patients who discontinue for lack of efficacy or rescue medication will be considered as treatment failures.

In cases of missing or incomplete dates (e.g. AE and concomitant medications), the missing component(s) will be assumed as the most conservative value possible. For example, AEs with missing start dates, but with stop dates either overlapping into the treatment period or missing, will be counted as treatment-emergent, taking the worst-case approach. When partial dates are present in the data, both a partial start date and/or a partial stop date will be evaluated to determine whether it can be conclusively established that the AE started prior to the start of study drug or ended prior to the start of study drug. If the above cannot be conclusively established based on the partial and/or present dates, then the AE will be considered as treatment-emergent. Actual data values as they appear in the original electronic Case report form (eCRF) will be presented in the data listings.

Missing values for other variables will not be imputed and only observed values will be used in data analyses and summaries.

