### 3.2.4 Mycological per-protocol (MPP)

The MPP population will include all randomized patient who had positive baseline culture for *Aspergillus spp* and/or *Candida spp* and who:

- Satisfied all inclusion and exclusion criteria;
- Did not receive any prohibited concomitant medications (except if it is considered rescue medication);
- Did not have any other major protocol violations;
- Completed Visit 2;
- Completed Visit 3 and Visit 4 (unless the subject was deemed a clinical failure at an earlier visit than Visit 4);
- Completed Visit 4 within the designated visit window;

- Had compliance rates between 80% and 100% as defined in Section 3.3.7 (patients who are deemed Clinical Failures are to be included if they had compliance rates between 80% and 100% during the first 3 days of study treatment);
- Had mycological results (when subject has material to culture) from Visit 1, Visit 2, Visit 3 and/or Visit 4 unless the subject was deemed a clinical failure at an earlier visit than Visit 4.

For the CITT and MITT populations, the treatment group of a patient will be determined by the treatment group to which the patient was randomized.

For the Safety and MPP populations, the treatment group of a patient will be determined by the treatment the patient received, not necessarily the group to which he or she was randomized. The Safety population will be used for all safety analyses.

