### 3.4.3 *Subgroups*

Analyses of primary efficacy variable will be performed for subgroups of patients based on baseline characteristics for the following:

- Age group (<65 years, ≥65 years)
- Sex (male versus female)
- Unilateral/bilateral
- Fungal infection/Fungal and bacterial infection/Bacterial infection

Any additional subgroup may be considered.

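### Rescue is defined by the recorded reason for treatment, so some prohibited antifungal or ear-drop use affecting the evaluable ear can still end as a therapeutic cure in the primary analysis

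*Protocol*

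**What the plan says.** **Prohibited drugs.** Protocol 6.7.1 prohibits "Any systemic antimicrobial or antifungal drug". It also prohibits anything put into or around the evaluable ear (apart from non-bacteriostatic saline for cleaning before sampling) and, with stated exceptions, systemic corticosteroids. These bans attach to the drug and the site; the reason for use plays no part. They are lifted once the patient has prematurely stopped study treatment.

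**Rescue.** Protocol 6.7.2 carves rescue out of the prohibited list: "Prohibited medication will be considered rescue medication if they meet both of the following criteria". The first criterion is "Any otic or systemic treatment administered for reasons associated with otomycosis of the evaluable ear", with a note that "topical products applied in the non-evaluable ear are NOT considered to be rescue medication". The second is "Started after Visit 1 but before or at Visit 4".

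**Failure rules.** Protocol 7.1.1.5 and SAP 2.3.1.1.5 make a patient who takes rescue, as defined in 6.7.2, a clinical failure. SAP 3.1.3 adds that "patients who discontinue for lack of efficacy or rescue medication will be considered as treatment failures", and counts missing or indeterminate outcomes as failures. Protocol 10.1.3 and SAP 3.4.1 say the same.

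**Cure and populations.** Therapeutic cure (Protocol 7.1.3, SAP 2.3.1.3) needs a total signs/symptoms score (TSSS) of 0 plus eradication or presumed eradication. It carries no medication condition. MITT membership depends only on the baseline culture. Prohibited drugs that are not rescue exclude a patient from the mycological per-protocol (MPP) set (Protocol 10.1.4, SAP 3.2.4). Prohibited drugs are also tabulated and listed (SAP 3.3.5).

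**The concern.** The plan restricts these drugs by what they are and where they go, because they could affect the ear being judged. The primary outcome rule alone switches to the reason written on the medication record. The same product in the same ear, or the same oral antifungal in a patient with two infected ears, then yields a failure or a possible cure according to that one entry. The phrase about reasons associated with otomycosis is not defined, so the entry is partly discretionary.

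At stake is whether the primary comparison credits an arm with cures to which another active drug may have contributed. Extra cures on placebo would dilute the difference. Extra cures on clotrimazole would inflate it, which is the worse error for a superiority claim.

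**Working it through.** **1. Tracing a patient through the rules.** Take a MITT patient who attends every visit and has TSSS 0 and no material to culture at Visit 4.

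| Treatment started between Visits 1 and 4 | Prohibited (6.7.1)? | Rescue (6.7.2)? | MITT outcome | MPP |
|---|---|---|---|---|
| Systemic antifungal, recorded for the evaluable ear | Yes | Yes | Failure | Not excluded for this drug |
| Same drug, recorded for otomycosis of the other ear only | Yes | No, first criterion not met | Cure | Excluded |
| Antifungal, antimicrobial or corticosteroid product in the evaluable ear, recorded for another reason | Yes | No, first criterion not met | Cure | Excluded |

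The note in 6.7.2 exempts only topical products in the other ear. It does not address a systemic drug given for that ear.

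No other rule intervenes. The patient is neither missing nor a lack-of-efficacy discontinuation. Protocol 5.3 requires study withdrawal when rescue is given, but expects patients who stop study drug without rescue to return for efficacy evaluation at Visits 3 and 4. With no material to culture and TSSS 0, mycological outcome is presumed eradication, so no culture stands in the way. The sensitivity analyses in SAP 3.4.1 deal with covariate adjustment and missing data, so they do not reach these patients.

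**2. Reproducing the design figure.** Inputs from Protocol 10.1.1 and 10.1.10.1: 100 clotrimazole and 50 placebo patients, 60% v 30%, two-sided 5% chi-square test.

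- Pooled rate = (60 + 15)/150 = 0.50. Null SE = √[0.50 × 0.50 × (1/100 + 1/50)] = 0.0866.
- Alternative SE = √(0.60 × 0.40/100 + 0.30 × 0.70/50) = 0.0812.
- Power = Φ[(0.30 − 1.96 × 0.0866)/0.0812] = 94.6%.
- Summing exact binomial probabilities over all tables where the uncorrected chi-square is significant in favour of clotrimazole gives 95.0%. The stated 95% is reproduced.

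**3. Size per patient.** One cure moves the placebo rate by 1/50 = 2 points and the clotrimazole rate by 1/100 = 1 point.

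**4. Illustrations.** Same exact method. The number of extra cures is my assumption, entered as a shift in the underlying rate.

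| Extra cures | Rates compared | Power |
|---|---|---|
| None | 60% v 30% | 95.0% |
| One on placebo | 60% v 32% | 91.8% |
| Three on placebo | 60% v 36% | 81.5% |
| One in each arm | 61% v 32% | 93.4% |
| Two on clotrimazole, one on placebo | 62% v 32% | 94.8% |

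In the other direction, suppose there is no true effect (30% in both arms). The chance of a significant result favouring clotrimazole is 2.4%. Two extra cures on clotrimazole only (32% v 30%) raise it to 4.2%, and five (35% v 30%) to 8.6%.

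**The case against.** **The cases may be rare.** For otomycosis that becomes bilateral, Protocol 8.1 and 8.2.2 provide a second kit of the same study medication, not a systemic antifungal. Known bacterial otitis externa and current infections needing systemic antimicrobial or antifungal therapy are excluded at entry (5.2). The planned subgroup "Fungal infection/Fungal and bacterial infection/Bacterial infection" is by baseline characteristics and does not predict antibiotic drops during the study. This stands: the documents leave the route open, but do not show that it will be used often.

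**The rescue wording can be read broadly.** In disease bilateral at baseline, the evaluable ear is the one with the higher score (the left if tied), so a systemic antifungal would often be attributable to it. That narrows the gap. It also leaves the classification to whoever records the reason.

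**Antibiotic drops are not shown to cure otomycosis.** A reader might infer that they would produce cures. Protocol 2.1 points the other way: it lists topical antibiotic/steroid use as a risk factor and stopping topical antibiotics as a treatment recommendation. This stands as to mechanism. The counting problem is that such a patient's outcome is accepted without any rule. A positive fungal culture would still make the patient a failure, but only where there is material to culture.

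**Existing handling would expose an imbalance.** Tabulation by arm and the MPP repeat help. However, the MPP drops these patients; it does not count them as failures, and it is not primary. A patient who leaves the study is indeterminate, hence a failure, but nothing requires withdrawal for a prohibited drug that is not rescue.

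**Ignoring treatment given for unrelated reasons is a defensible MITT choice.** This stands for systemic drugs given for infection elsewhere, where failing every patient is a trade-off. It is weaker for a product put into the evaluable ear, or a systemic antifungal given for otomycosis itself.

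**Conclusion.** The gap is real and follows from the text: in the primary analysis, two kinds of prohibited treatment that reach or may reach the evaluable ear can end as a failure or a cure depending on the recorded reason. No figure in the plan is wrong.

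The size cannot be estimated, because the documents give no expected frequency. Each case is worth 2 points on placebo or 1 point on clotrimazole. If all extra cures fall on placebo, one costs about 3 points of power (95.0% to 91.8%) and three cost about 13 (to 81.5%). One in each arm leaves 93.4%.

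A reader might infer that such use would be commoner on saline and so always dilute the effect. The documents do not support that: they say nothing about frequency by arm, and extra cures on clotrimazole would inflate the effect. The placebo-only figures are illustrations, not predictions.

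**What to change.** Change outcome counting only.

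- **Primary rule, SAP 3.1.3 and 3.4.1.** Keep rescue as a failure. In addition, for the cure endpoints, count as failure (a) any antifungal, antimicrobial or corticosteroid product put into the evaluable ear and (b) any systemic antifungal given for otomycosis of either ear, where started after Visit 1 and before the Visit 4 assessment, whatever reason is recorded for the evaluable ear.
- **Assignment.** Identify the cases at the blind data review already planned before database lock (SAP 3.3.2), using the recorded and coded concomitant medications.
- **Sensitivity analyses.** Report the present indication-based rule as one. As another, report a broader rule that also counts as failures patients given systemic antifungals, antimicrobials or corticosteroids prohibited under 6.7.1 for unrelated reasons.
- **Reconcile Protocol 6.7.1 and 6.7.2.** The first lifts the prohibitions after premature discontinuation of study treatment, while the second defines rescue as a subset of prohibited drugs. Read literally, nothing taken after stopping study drug is rescue, yet Protocol 8.2.2 treats rescue prescribed at that point as treatment failure.

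The cost is a few lines of SAP text, a medication-code rule and two further tables. The downside is that a few patients, in either arm, become failures although their ear may have cleared on study drug alone. No change to what may be prescribed is proposed.

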6.7.3 Recommended Concomitant Analgesics

For patients who require analgesic medications for otalgia, the recommended medication is acetaminophen (paracetamol). The use of acetaminophen should never be considered as an initial treatment for otalgia, thus will only be administered after confirming that the study medication is not sufficient for pain relief.

